## 1 PROTOCOL SYNOPSIS

**SPONSOR:** Sanguine Biosciences, Inc.

**STUDY TITLE:**

A Single-Site Tissue Repository Providing Annotated Biospecimens for Approved Investigator-directed Biomedical Research Initiatives

**PROTOCOL NUMBER:** SAN-BB-02

**PRIMARY OBJECTIVE:**

To collect, preserve, and/or distribute annotated biospecimens and associated medical data to institutionally approved, investigator-directed biomedical research to discover and develop new treatments, diagnostics, and preventative methods for specific and complex conditions.

**STUDY DESIGN:**

- A single-site, cross-sectional study
- Biological tissue samples will be collected from study participants, processed, and preserved in the biorepository's cryogenic core biobank (hereinafter, "biobank") until a research study requests a sample.
- If a sample does not require processing, the sample may be delivered directly to the requesting researchers or designated third parties.
- Health information will be collected via self-report and medical record review to obtain a detailed clinical history of the participant's health. This information includes but is not limited to demographic and lifestyle information, current medications and comorbidities, date of diagnosis, condition-related treatment history, current disease characteristics, diagnostic reports, and family medical history.
- Sanguine will implement a software-as-a-service (SaaS) provider of electronic signature technology and transaction management solutions or a hardcopy of the informed consent form (ICF). Participants may electronically sign the ICF and authorization of release of information using an electronic device. The Sponsor may alternatively provide the participant the option of completing hardcopy documents if they so desire. In addition to the Principal Investigator (PI), approved study staff can also administer and sign the ICF and will address all of the participant's queries regarding the ICF and study design.
- All participants biospecimens, if processed, will be stored and distributed by blinded personnel to the participants direct identifiers.

## **DURATION OF PARTICIPANT PARTICIPATION:**

- This study requires the collection of a tissue sample, which is considered active participation. Study enrollment and the sample collection take about one hour or more to complete depending on the number and types of samples collected. Therefore, active participation will be about one hour and may be up to two hours.
- Inactive participation lasts as long as a participant's samples and data remain at the biobank. There is no limit on the length of time samples and data may be stored. The samples may remain indefinitely at the biobank or until the participant decides to withdraw their participation from the study.

## **STUDY POPULATIONS:**

### **Health Condition Group:**

#### **Health Condition Group Inclusion Criteria:**

- Persons 18 to 85 years of age at the date of informed consent.
- If presenting with a history of a specific condition, the diagnosis is confirmable in the medical record or may be confirmed using other forms of verification including self-reporting.
- Understands the procedures and requirements of the study by providing written informed consent (or verbal assent if a legally authorized representative will sign the ICF), including consent for authorization for protected health information disclosure.

#### **Health Condition Group Exclusion Criteria:**

- Persons younger than 18 years of age or older than 85 years of age at the date of informed consent.
- Receipt of blood products 30 days before the study blood draw.
- Receipt of an investigational (unapproved) drug 30 days before the study blood draw.
- A confirmable diagnosis of any medical condition that would increase potential phlebotomy risks. Such medical conditions include:
  - Severe or untreated cardiovascular diseases;
  - Bleeding disorders;
  - Late-stage chronic kidney disease; and/or
  - Conditions associated with chronic anemia.
  - Stage 3 and 4 cancers
- Pregnancy
- Has donated a unit of blood within the last 2 months at the date of informed consent.

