### **Exceptional Condition Group:**

#### **Exceptional Condition Group Inclusion Criteria:**

- Persons 18 to 85 years of age at the date of informed consent
- If presenting with a history of a specific condition, the diagnosis is confirmable in the medical record.
- A confirmable diagnosis of any medical condition that would increase potential phlebotomy risks. Such medical conditions include:
  - Severe or untreated cardiovascular diseases; (including a stroke or myocardial infarction within the last 2 months)
  - Bleeding disorders;
  - Late-stage chronic kidney disease;
  - Splenomegaly;
  - Pregnancy; and/or
  - Conditions associated with chronic anemia.
- Understands the procedures and requirements of the study by providing written informed consent (or verbal assent if a legally authorized representative will sign the ICF), including consent for authorization for protected health information disclosure.

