#### **Health Condition Group Exclusion Criteria:**

- Persons younger than 18 years of age or older than 85 years of age at the date of informed consent.
- Receipt of blood products 30 days before the study blood draw.
- Receipt of an investigational (unapproved) drug 30 days before the study blood draw.
- A confirmable disease of any medical condition that would increase potential phlebotomy risks. Such medical conditions include:
  - Severe or untreated cardiovascular diseases;
  - Bleeding disorders;
  - Late-stage chronic kidney disease; and/or
  - Conditions associated with chronic anemia.
- Pregnancy
- Has donated a unit of blood within the last 2 months at the date of informed consent.

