#### **5.3.3 Potential Participant Cohort Placement**

After the screening process, trained study staff will review the self-reported medical history to determine cohort placement. If the participant does not report any medical conditions or remarkable medical history, they will be placed in the control cohort. If the participant has reported a medical condition that could potentially increase the presentation of risks associated with phlebotomy, such as bleeding disorders, severe or untreated cardiovascular diseases, late-stage chronic kidney diseases, pregnancy, or splenomegaly, the participant will be placed in the exception condition cohort. This cohort identification is designed to distinguish participants who require additional protection during a phlebotomy procedure. All other participants will be placed

in the health condition group. If a participant does not meet inclusion/exclusion criteria, they will be notified that they cannot participate in this study.

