**Table 1: Maximum Blood Collection Volume by Cohort**

Cohort	Blood Draw Volume (mL)
Health Condition	≤100mL
Exceptional Condition	≤60mL
Control	≤180mL

The maximum blood collection volume within a 6-week period by cohort.

Participants within the health condition and control groups who weigh less than 110 pounds and/or are older than 85 years old will have a maximum collection volume of 75mL within a 6-week period.

Before the phlebotomy procedure, a Sanguine designated phlebotomist will assess the participants health by asking questions like, “Do you feel healthy today?” and noting any physical symptoms that may require the blood draw to be aborted. The phlebotomist then decides if the blood draw can continue as scheduled. The blood draw appointment follows phlebotomy best practices set forth by the College of American Pathology (CAP) and the World Health Organization (WHO). Venipuncture is attempted no more than 3 times. After a third failed attempt, the blood draw is canceled. After the blood draw, the phlebotomist will remain with the participant until the wound has successfully clotted and/or the participant reports that they feel well enough to resume light activities.

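### The two Health Condition Group exclusion lists disagree on stage 3 and 4 cancers, so the cohort of these donors, and with it their blood-volume cap, is left to staff judgement

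*Protocol*

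**What the plan says.** The Health Condition Group has two current exclusion lists. The synopsis list ends its phlebotomy-risk conditions with "Stage 3 and 4 cancers". The list in Section 5.2.1 opens with "A confirmable disease of any medical condition that would increase potential phlebotomy risks. Such medical conditions include" and stops at chronic anemia, with no cancer item.

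The Exceptional Condition Group (called Exceptive in Section 5.2.2) admits donors under the criterion "A confirmable diagnosis of any medical condition that would increase potential phlebotomy risks. Such medical conditions include", worded alike in the synopsis and in 5.2.2. Neither version names cancer.

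Under Section 5.3.3, "trained study staff will review the self-reported medical history to determine cohort placement". Its stated purpose is protective: "This cohort identification is designed to distinguish participants who require additional protection during a phlebotomy procedure". A donor who reports a condition that could raise phlebotomy risk goes to the exception cohort, with examples that do not include cancer. A donor who reports no condition goes to the control cohort. "All other participants will be placed" in the Health Condition Group.

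Table 1 then sets "The maximum blood collection volume within a 6-week period by cohort": 100 mL for Health Condition, 60 mL for Exceptional Condition and 180 mL for Control. Health Condition and control donors who "weigh less than 110 pounds and/or are older than 85 years old will have a maximum collection volume of 75mL" per 6 weeks.

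**The concern.** Cohort is the protocol's device for picking out donors who need extra care during a blood draw, and it fixes the volume ceiling. The synopsis itself classes stage 3 and 4 cancer as a phlebotomy risk. A coordinator who reads Section 5.2.1, 5.2.2 or 5.3.3 is not told this and must decide unaided whether advanced cancer counts.

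Two trained staff members could therefore place the same donor in different cohorts, and each could point to protocol text in support. The one who does not see a risk would reach the residual rule in 5.3.3 and apply the higher ceiling. Cancer donors are a realistic case: Section 2 discusses oncology at length, and the example health profile in Appendix C has cancer fields.

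**Working it through.** **Step 1. Set the lists side by side.** Each column is one list of conditions treated as raising phlebotomy risk.

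| Condition | Synopsis, Health Condition exclusion | 5.2.1 exclusion | Synopsis, Exceptional inclusion | 5.2.2 inclusion | 5.3.3 examples |
|---|---|---|---|---|---|
| Severe or untreated cardiovascular disease | yes | yes | yes | yes | yes |
| Bleeding disorders | yes | yes | yes | yes | yes |
| Late-stage chronic kidney disease | yes | yes | yes | yes | yes |
| Chronic anemia conditions | yes | yes | yes | yes | no |
| Splenomegaly | no | no | yes | yes | yes |
| Pregnancy | separate item | separate item | yes | yes | yes |
| Stage 3 and 4 cancers | **yes** | **no** | no | no | no |

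The cancer item appears in one list of five. It is also the only row in which the synopsis and body versions of the same group's list differ.

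**Step 2. Trace a donor who reports stage 3 or 4 cancer.**

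- Control is not in play, because the donor reports a medical condition.
- If staff treat the cancer as a phlebotomy risk, as the synopsis does, 5.3.3 sends the donor to the Exceptional group and both Exceptional lists admit the donor through their open wording.
- If staff do not, nothing in 5.2.1, 5.2.2 or 5.3.3 corrects them by name, and the residual rule gives the Health Condition Group.

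**Step 3. Compare the caps (Table 1, per 6-week period).**

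- Donor of 110 lb or more: 100 − 60 = 40 mL; 100 / 60 = 1.67.
- Donor under 110 lb: 75 − 60 = 15 mL; 75 / 60 = 1.25.

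The age part of the 75 mL rule does not bear on this, since persons over 85 are not eligible.

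**Step 4. Check whether stage is visible at placement.** The Appendix C profile shows a cancer field and a cancer-type field but no stage field. It is only an example. The synopsis says that current disease characteristics and diagnostic reports are collected, without saying when. Whether staff know the stage before they assign a cohort cannot be settled from the protocol.

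**The case against.** The best defence is that the rule is the same everywhere and only the examples differ. Every list covers any condition that raises phlebotomy risk and then illustrates it. Splenomegaly and chronic anemia also come and go between lists, so a missing example is weak evidence of a different rule. Much of this stands. A reader might infer that Section 5.2.1 permits stage 3 and 4 cancer in the Health Condition Group; it does not say so, and its open wording can exclude it. But the splenomegaly and anemia gaps lie between different groups or sections, whereas the cancer gap lies between two versions of one group's list. Open wording lets staff reach the right cohort without requiring it.

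A second defence is that other controls apply. Section 4.1 has health assessed before the draw to set the maximum volume in every cohort, Section 5.3.5.1 ties volume to self-reported medical data as well as cohort, and Section 5.2 puts a medical doctor over eligibility and medical history. This stands too. These controls make an excess draw less likely, though they do not say which cohort applies.

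A reader might also take 5.2.1 as the section staff work from, so that its omission decides practice. The protocol gives no order of precedence between synopsis and body, so that step is unsupported.

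**Conclusion.** The mismatch is real: one current list names stage 3 and 4 cancers as a phlebotomy risk, its counterpart does not, and the Exceptional lists and placement examples are silent. It deserves a minor safety and eligibility clarification. Objectives, sample size and analysis are untouched.

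It is tempting to say that the protocol sets 60 mL for these donors and that 5.2.1 breaches it. The documents do not go that far. The 60 mL cap is an inference: the synopsis classes the condition as a phlebotomy risk, and such risk is the entry criterion for the Exceptional group. If the sponsor did not intend the synopsis line, there may be no excess at all.

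The differences of 40 mL and 15 mL are therefore differences between ceilings, not expected volumes drawn. They rest on three conditions: the synopsis line is intended, staff do not judge advanced cancer a risk, and neither the pre-draw assessment, the self-reported data nor the overseeing doctor corrects the placement or volume. The number of donors with stage 3 or 4 cancer is not given, so the frequency cannot be estimated.

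**What to change.** Add stage 3 and 4 cancers to the exclusion list in Section 5.2.1, and name them in the synopsis Exceptional list, Section 5.2.2 and the placement examples in Section 5.3.3, so that the 60 mL cap applies without inference. Only if the sponsor's medical reviewer says that the synopsis line was not intended, delete that line instead.

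The cost is four added lines in one amendment, or one deleted line, with no new procedure.

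Ask the sponsor to confirm that cancer stage is asked before cohort placement. If it is not, a stage question at screening is needed for the criterion to work.

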### **Exceptional Condition Group:**

#### **Exceptional Condition Group Inclusion Criteria:**

- Persons 18 to 85 years of age at the date of informed consent
- If presenting with a history of a specific condition, the diagnosis is confirmable in the medical record.
- A confirmable diagnosis of any medical condition that would increase potential phlebotomy risks. Such medical conditions include:
  - Severe or untreated cardiovascular diseases; (including a stroke or myocardial infarction within the last 2 months)
  - Bleeding disorders;
  - Late-stage chronic kidney disease;
  - Splenomegaly;
  - Pregnancy; and/or
  - Conditions associated with chronic anemia.
- Understands the procedures and requirements of the study by providing written informed consent (or verbal assent if a legally authorized representative will sign the ICF), including consent for authorization for protected health information disclosure.

#### **Exceptional Condition Group Exclusion Criteria:**

- Persons younger than 18 years of age or older than 85 years of age at the date of informed consent.
- Receipt of blood products 30 days before the study blood draw.
- Receipt of an investigational (unapproved) drug 30 days before the study blood draw.
- Has donated a unit of blood within the last 2 months at the date of informed consent.

### **Control Group:**

#### **Control Group Inclusion Criteria:**

- Persons 18 to 85 years of age at the date of informed consent.
- Understands the procedures and requirements of the study by providing written informed consent (or verbal assent if a legally authorized representative will sign the ICF), including consent for authorization for protected health information disclosure.

### **Control Group Exclusion Criteria:**

- Persons younger than 18 years of age or older than 85 years of age at the date of informed consent.
- Receipt of blood products 30 days before the study blood draw.
- Receipt of an investigational (unapproved) drug 30 days before the study blood draw.
- A confirmable diagnosis of any medical condition that would increase potential phlebotomy risks. Such medical conditions include:
  - Severe or untreated cardiovascular diseases;
  - Bleeding disorders;
  - Late-stage chronic kidney disease; and/or
  - Conditions associated with chronic anemia.
- Pregnancy
- Requires a Legally Authorized Representative (LAR) for the study informed consent.
- Has donated a unit of blood within the last 2 months at the date of informed consent.

### **STUDY OUTCOMES**

The study's objective is to provide quality and standardized biospecimen collections to the biomedical community to facilitate future personalized medical care.

### **SAMPLE SIZE CONSIDERATIONS**

The number of participants to be enrolled in this study is 20,000. The reason for 20,000 participants is that the Sponsor anticipates that over 2 years of the study, at least 50% of the participants will discontinue study participation. Because this study aims to establish a tissue biorepository for future therapeutic and diagnostic research endeavors, the Sponsor requires accrual and maintenance of a large enough biospecimen cohort for research clients to obtain statistically significant results. Therefore, the Sponsor believes that this sample size will provide the required sample diversity and volume to achieve statistically significant results despite participation attrition.

## 2 BACKGROUND & RATIONALE

To collect, preserve, and/or distribute annotated biospecimens and associated medical data to institutionally approved, investigator-directed biomedical research to discover and develop new treatments, diagnostics, and preventative methods for specific and complex conditions.

Biomedical research has utilized biorepository specimens for decades. Starting as small, private tissue collections, investigators analyzed small cohorts of samples to validate an anticipated molecular or genetic aberration specific to a particular disease. In recent years, advances in molecular and genetic research techniques have extended the ceiling of biomedical research potential allowing large volumes of samples, genes, and molecules surrounding a disease to be analyzed quickly and cost-effectively. One major factor now governing translational research is the availability of quality biospecimens to deliver quality results.

The National Cancer Institute surveyed over 700 investigators regarding their research experience with biobank specimens. Over 60% of researchers surveyed considered the specimens to be under-annotated, 47% stated the quality was questionable. This led to 60% of researchers questioning their findings and over 80% were forced to limit the scope of their proposed research. It is evident that the quality of research conducted using biobank specimens would be greatly enhanced by standardized collection and storage processes assuring the uniform quality of the material to be studied.

Another factor hindering the clinical applicability and impact of biomedical research findings is the limited volume and diversity of available samples for analysis. Traditional institutionally established biobank collections are restricted by regional location and the population. Such biobanks are also limited to collect specimens from people seeking medical care. Analyzing molecular patterns present within these collections limits the applicability of investigational findings.

A third issue limiting the scope of current molecular and genetic research methods is the sheer complexity of health conditions, both etymologically and in terms of therapeutic efficacy. Researchers have exhausted the effects of one to a few genes on a disease state. When mutated, a single gene can trigger a rare inherited disorder such as Huntington's disease, which is an increasingly infrequent discovery. Many diseases are increasingly viewed as complex conditions affected by numerous genes of varying influence. In oncology alone, there are more than 100 known types of cancer, mostly named after the organs they were first located and the type of cells from which they originate. Yet, these common pathological designations are rapidly becoming less definitive as molecular markers become more clinically relevant in the era of personalized medicine. The National Comprehensive Cancer Network (NCCN) has more than forty molecular biomarkers for clinical practice to characterize six of the most common types of malignancies. The NCCN has designated an entire task force to vet the increasing number of potential markers for clinical use.

Molecular markers can be diagnostic, prognostic, or predictive and are revolutionizing cancer treatment through the elucidation of genetic factors, which can influence a participant's specific therapeutic course. Cancer is comprised of hundreds of distinct molecular diseases. The ability to molecularly distinguish cancer types independent of routine gross and microscopic inspection holds the potential for discovering therapeutic similarities between well-documented and

uncommon types of cancer. This may increase participant outcomes for rare forms of cancer. An example of this is imatinib; a drug approved by the FDA to treat leukemia. Researchers discovered molecular similarities between leukemia and gastrointestinal stromal tumors (GIST), making tumors responsive to imatinib. This molecular correlation proved correct in clinical trials, and imatinib was FDA-approved to treat GIST.

Cancer is one of many fields exploring genetic and molecular variability between disease subtypes and individuals. Autoimmune, metabolic, cardiovascular, and most other common and rare health conditions are influenced by genetic predisposition and environmental and comorbid factors. Common conditions such as atherosclerosis or diabetes mellitus are caused by deficiencies in multiple genes combined with diet or lifestyle habits. Because each gene contributes a small amount to overall risk, varying signals are emitted, confounding efforts to associate it with a specific disease state. Therefore, researchers need to study the genetic profiles of many people, incorporating phenotypic and health data to maximize clinical impact. In addition to the molecular complexity of the pathophysiology of health conditions, treating diseases can be just as complex. It is well known that standards of treatment do not consistently work from participant to participant. Therefore, to more effectively treat participants, physicians must understand the genetic complexity associated with certain medical conditions and the individual. To decipher the genetic web that governs certain conditions, researchers must study a large and diverse cohort of genetic material to arrive at statistically significant results.

